Data from the study will be maintained for two (2) years after the date the investigation is completed, terminated or until the records are no longer required to support the protocol, whichever date is later. Patient records and data are eligible for inspection and/or copying by applicable regulatory authorities.

Expected outcomes.

It is the expectation that both hydroxyapatite and brushite-containing toothpastes will show improved patient outcomes over negative control. Improvements in tooth hypersensitivity, enamel acid resistance, and remineralisation rate are expected from the study and positive control groups compared to the negative control group. Data interpretation and the statistical significance of the results will be described later in this protocol.

Adverse reactions.

There is no expectation of any adverse outcomes or reactions due to a patient using the assigned toothpastes. However, hypersensitivity reactions to some of the toothpastes' components are still possible. All participants will be given access to contact info of the investigators. Any adverse reactions should be reported immediately to the investigators.

Reasons for Withdrawal or Termination

A subject may be discontinued from the study at any time if the subject or the Investigator feels that it is not in the subject's best interest to continue. The following is a list of possible reasons for study treatment discontinuation:

- Screening Failure
- · Subject withdrawal of consent
- Subject is not compliant with study procedures
- Adverse Event that in the opinion of the Investigator would be in the best interest of the subject to discontinue study participation
- Protocol violation requiring discontinuation
- Lost to follow-up

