All subjects are free to withdraw from participation at any time, for any reason, specified or unspecified, and without prejudice. Reasonable attempts will be made by the Investigator to provide a reason for subject withdrawals. The reason for the subject's withdrawal from the study will be specified in the subject's source documents and the Case Report Form (CRF). If a subject is withdrawn from treatment due to an AE (adverse Event), the subject will be followed and treated by the Investigator until the abnormal parameter or symptom has resolved or stabilized. The Investigator must make every effort to contact subjects who are lost to follow-up. Attempts to contact such subjects must be documented in the subject's records (e.g., times and dates of attempted telephone contact, receipt for sending a registered letter, etc.).

Handling of Participant Withdrawals of Termination:

Although subjects may withdraw from the study at any time and for any reason, (or may be withdrawn at the Investigator's discretion), subject withdrawal should be avoided as much as reasonably possible. In any case, appropriate follow-up for endpoints should be continued. Subjects who prematurely discontinue are not to be replaced. For subjects considered lost to follow-up, the CRF must be completed up to the last visit performed.

Premature Termination or Suspension of Study:

This study may be temporarily suspended or prematurely terminated if there is sufficient reasonable cause. Written notification, documenting the reason for study suspension or termination, will be provided by the suspending or terminating party to the Investigator and the Institutional Review Board (IRB), as appropriate. If the study is prematurely terminated or suspended, the Investigator will promptly inform the IRB and will provide the reason(s) for the termination or suspension.

Circumstances that may warrant termination or suspension include, but are not limited to:

- Determination of unexpected, significant, or unacceptable risk to participants
- Demonstration of efficacy that would warrant stopping
- Insufficient compliance to protocol requirements
- Data that are not sufficiently complete and/or evaluable
- Determination of futility

Study may resume once concerns about safety, protocol compliance, data quality are addressed and satisfy the IRB.

Methods and Study Schedule:

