Early Termination

All subjects have the right to withdraw from study participation at any time during the study. If, for whatever reason, a subject withdraws from the study, an Early Termination visit will be performed.

The following procedures will be performed (if agreed upon by the subject) at the Early Termination visit:

- Assess for adverse events
- Assess for complications following treatments
- Document all current medications, including medications over-the-counter and herbal medications

RANDOMIZATION

Subjects who meet all inclusion and exclusion criteria will be randomized on Treatment Day in a 1:1:1 ratio to either the Study Group or the Positive or Negative Control Group, in accordance with a computer-generated schedule prepared by a third-party person, who will not participate in the study. Study personnel will be instructed not to randomize until subject has been confirmed to meet all inclusion/exclusion criteria on treatment day.

SAMPLE SIZE JUSTIFICATION

Sample Size Calculations

The sample size was determined according to the previous trial by the same authors, where Shiff index was assessed. The power was set at 80%, alfa-level was set as 0.05, the means from the previous study were 2.6±0.75 and 1.9 in toothpaste and placebo groups, respectively. The allocation ratio was equal to 1. The target sample size comprised 18 participants in each group, 54 patients total.

STATISTICAL ANALYSIS PLAN

Primary Endpoint

Tooth hypersensitivity as measured with Shiff's index

Secondary Endpoints

Enamel mineralisation characteristics as measured by enamel acid resistance test and rate of enamel remineralisation.

All analyses will be performed using per-protocol population as well as intention-totreat population (to include subjects who are withdrawn prematurely or randomized but not treated per randomization arm).

ASSESSMENT OF SAFETY

Adverse events (AE) will be monitored and collected by the study team from the point of signed consent until 7 (for non-serious AEs) or 30 days (for serious AEs, SAEs) after the last day of study participation. For each AE, a detailed explanation will be obtained from the subject and subject's medical record. All AEs will be recorded on the CRFs.

Definition of Adverse Event

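### The stated 80% power at 18 per arm belongs to one undeclared two-arm contrast with complete data, in a three-arm trial that expects two active pastes to beat control

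*Protocol*

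**What the plan says.** Under Sample Size Calculations, the protocol bases the number on an earlier trial's Schiff index: "The power was set at 80%, alfa-level was set as 0.05", and "the means from the previous study were 2.6±0.75 and 1.9 in toothpaste and placebo groups, respectively". It adds that "The allocation ratio was equal to 1" and concludes: "The target sample size comprised 18 participants in each group, 54 patients total".

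The Randomization section describes three arms, allocated "in a 1:1:1 ratio to either the Study Group or the Positive or Negative Control Group". Under Expected outcomes, "It is the expectation that both hydroxyapatite and brushite-containing toothpastes will show improved patient outcomes over negative control". On withdrawals, "Subjects who prematurely discontinue are not to be replaced".

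The synopsis gives the decrease in hypersensitivity after the brushite paste as the primary objective and does not mention hydroxyapatite there. The section headed Statistical Analysis Plan names the Schiff index as primary endpoint and lists per-protocol and intention-to-treat populations. It names no primary contrast or time point. Schiff is measured at baseline, 2 weeks and 4 weeks. The Study Design paragraph says sixty people were randomly assigned; the synopsis, the arm descriptions and the sample size section say 54, or 18 per arm.

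**The concern.** A power figure means something only for a stated comparison. Here the inputs describe one toothpaste group against one placebo group, and the resulting 18 is then applied to each of three arms. The only expectation that the protocol writes down involves two comparisons with the negative control. The calculation has no allowance for a second comparison or for losses.

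A reader could therefore take 80% as the chance of seeing the expected result, when it is the chance of one of its two parts under ideal follow-up. The false-positive side is open too: with no primary contrast declared, a win by either paste at 0.05 could be presented as the trial's success.

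**Working it through.** **Inputs from the protocol.** Difference 2.6 − 1.9 = 0.7. SD 0.75, given for one group and assumed common. Alpha 0.05, with sidedness not stated; two-sided is assumed because it reproduces 18 (one-sided gives 15). Ratio 1.

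**Assumptions not in the protocol.** The loss rate, the baseline to follow-up correlation r, and the same effect of 0.7 for both active pastes. The protocol does not say whether the two means are follow-up scores or changes; they are treated as follow-up scores.

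**1. Reproduce the stated figure.** n per arm = 2 × [0.75 × (1.960 + 0.842) / 0.7]² = 18.02. At n = 18 the standard error is 0.75 × √(2/18) = 0.25, so the standardised effect is 0.7 / 0.25 = 2.80. Normal power is Φ(2.80 − 1.96) = 79.96%. The 18 is thus a single two-arm comparison with no losses.

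**2. Same comparison by t-test (noncentral t).**

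| n per arm | Critical t | Noncentrality | Power |
|---|---|---|---|
| 16 | 2.042 | 2.640 | 72.4% |
| 18 | 2.032 | 2.800 | 77.6% |
| 19 | 2.028 | 2.877 | 79.9% |
| 20 | 2.024 | 2.951 | 82.0% |

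Going from 18 to 16 is a loss of 2/18 = 11%.

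**3. Two comparisons sharing one control, 18 per arm, no baseline adjustment.** The two test statistics have correlation 0.5 through the shared arm.

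- Rule A, both pastes must win at 0.05 each: 68.7% by bivariate normal, 65.5% by simulated t-tests (58.7% at 16 per arm). No alpha adjustment is needed.
- Rule B, either win counts at an unadjusted 0.05: family-wise error 9.1% by simulation. For two independent tests it would be 1 − 0.95² = 9.75%. The chance of at least one win is about 90%.
- Rule B with Bonferroni, 0.025 per comparison: 67.5% for each single comparison by t-test.

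**4. Baseline adjustment, 18 per arm, complete data.** The residual SD is 0.75 × √(1 − r²).

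| Assumed r | Residual SD | One contrast | Both pastes win |
|---|---|---|---|
| 0.3 | 0.715 | 81.4% | 70.6% |
| 0.5 | 0.650 | 88.1% | 80.4% |

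**5. The number randomised.** 60 / 3 = 20 per arm, and 20 × 0.9 = 18. So 60 would leave 18 per arm after a 10% loss, but the protocol never gives this as the reason for 60.

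**6. Direction of the means.** The protocol's Schiff scale runs from 0 (no reaction) to 3 (severe pain), yet the toothpaste group has the higher mean. Only the absolute difference enters step 1, so n is unaffected.

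**The case against.** The strongest reply is that brushite against negative control is the evident primary contrast. The synopsis objective names only that paste, and the sample size inputs are one toothpaste against placebo. On that view about 80% is the right figure before losses, and no multiplicity correction is due. This largely stands. The Expected outcomes text is an expectation and sets no success rule, so one cannot say that the trial is designed to require two wins. What remains is that the protocol never declares the contrast, so its power figure is not tied to one.

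The gap between 77.6% and 80% is small. It is the difference between a normal approximation and a t-test, and pooling the error over three arms gives 78.4%. On its own it would not merit a comment.

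Losses are assumed, since the documents give no rate. The protocol asks that endpoint follow-up continue after withdrawal, so a leaver need not be missing. Against that, the Early Termination visit lists no Schiff test.

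Two stronger readings are tempting. A reader might infer that the trial ignores its baseline score. That is true of the sample size calculation only: no analysis model is stated, the objective is worded as a decrease, and a covariate may sit in an analysis plan that is not shown. A reader might also combine the 65%, the 9% and the Bonferroni figure into one larger deficit. They belong to different decision rules. Reporting a per-protocol analysis beside intention-to-treat is routine and no defect in power.

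**Conclusion.** The concern holds in limited form. The stated 80% is correct arithmetic for one two-arm, unadjusted, complete-data comparison by normal approximation. It is not a statement about the three-arm trial or its written expectation. On the protocol's own inputs the figure is 77.6% by t-test for one contrast, 72.4% at 16 per arm, and about 65% if both pastes must beat control. Alternatively, if either win counted without adjustment, the family-wise error would be about 9%.

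These figures rest on two-sided testing, a common SD of 0.75, an equal effect for both pastes, no baseline adjustment and, for 16 per arm, an assumed loss. The documents do not show that the trial is too small. With baseline adjustment at r of about 0.5, 18 per arm gives about 80% even for both pastes winning, before losses. Nor does the higher mean for toothpaste show that harm was assumed; it shows that the labels, or what the means measure, need checking. The power statement should be corrected, but the design need not change.

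**What to change.** 1. Declare brushite against negative control on the Schiff score at week 4 as the single primary contrast, in line with the synopsis objective. Week 4 is proposed because it is the final visit; the investigators should confirm it. Test hydroxyapatite against negative control after it, for example in fixed order at two-sided 0.05, or report it as secondary. The fixed order is one reasonable option among several.
2. Restate the power at 18 per arm without baseline adjustment: about 78% for the primary contrast with complete data, about 72% at 16 per arm, and about 65% for both pastes winning.
3. Analyse the Schiff score adjusted for baseline Schiff, and give the power for that analysis beside the unadjusted figures: for one contrast with complete data, about 81% at an assumed correlation of 0.3 and 88% at 0.5. If the quoted SD proves to be that of a change score, these two figures need recalculating.
4. Reconcile 60 with 54 and say whether the difference is a loss allowance. Check the labels of the two means and what they measure.

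The cost is wording and one standard covariate, with no added patients or visits. The unadjusted power reads slightly less favourably, and under a fixed order hydroxyapatite is formally tested only if brushite succeeds.
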